10.4.3 Missing Data

The primary analysis will be completed on the FAS with available data per subject, assuming the overall study discontinuation rate is $<5\%$. If the overall study discontinuation rate is $\geq 5\%$ then the primary analysis will be based on the primary imputation methodology as defined [Section 10.4.5](#) and the available data analyses will become robustness analyses.

Additionally, robustness analyses will include repeating the primary analysis on the per protocol set (PPS); the FAS imputing missing data using last observation carried forward (LOCF); the FAS imputing missing data using Markov Chain Monte Carlo (MCMC) multiple imputation methodology under different assumptions of missingness (at random and not at random) each using 30 imputed values.

The imputation model, for each visit, under the assumption of missing **at random** is:

```
PROC MI DATA=INDATA SEED=97656 OUT=OUTDATA1 MINIMUM = 0 MAXIMUM = 3 ROUND  
= 1 NIMPUTE=30;  
  MCMC INITIAL=EM;  
  BY <TREATMENT>;
```

```
VAR <BASELINE> <PARAMETER>;
RUN;
where PARAMETER has 5 levels and refers to the corneal fluorescein staining
score for each region (inferior, superior, central, temporal, and nasal).
The imputation model, for each visit, under the assumption of missing not at
random is:
PROC MI DATA=INDATA SEED=36797 OUT=MDATA MINIMUM = 0 MAXIMUM = 3 ROUND =
1 NIMPUTE=30;
  MCMC IMPUTE=MONOTONE;
  VAR <BASELINE> <PARAMETER>;
RUN;

PROC MI DATA=MDATA SEED=38549 OUT=OUTDATA2 MINIMUM = . 0 0
  MAXIMUM = . 3 3 ROUND = . 1 1;
  CLASS <TREATMENT>;
  MONOTONE REG(<PARAMETER> = <BASELINE> / DETAILS);
  MNAR MODEL(<PARAMETER> / MODELOBS=(<TREATMENT>='Saline'));
  VAR <TREATMENT> <BASELINE> <PARAMETER>;
RUN;
```

where PARAMETER has 5 levels and refers to the corneal fluorescein staining score for each region (inferior, superior, central, temporal, and nasal).

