10.4.5 Primary Efficacy Analyses

The primary comparisons in this trial will be between NOV03 versus saline at Day 57 in the FAS with available data per subject using the following estimands:

- Population: Subjects with DED defined through enrollment criteria
- Endpoint:
 - CFB in tCFS in the study eye at Day 57
 - CFB of Dryness Score (VAS) at Day 57
- Intercurrent event:
 - Discontinuation of study medications is ignored. [treatment policy strategy]
 - Non-optimal compliance is ignored. [treatment policy strategy]

- Withdrawal due to any reason. Missing data not imputed. [hypothetical strategy]
- Population-level summary:
 - Difference in the mean CFB in tCFS in the study eye at Day 57 between NOV03 and saline.
 - Difference in the mean CFB of Dryness Score (VAS) at Day 57 between NOV03 and saline.

If the overall study discontinuation rate is $\geq 5\%$ then the primary analysis will be based on imputation methodology using the following estimands and the available data analyses will become robustness analyses.:

- Population: Subjects with DED defined through enrollment criteria
- Endpoint:
 - CFB in tCFS in the study eye at Day 57
 - CFB of Dryness Score (VAS) at Day 57
- Intercurrent event:
 - Discontinuation of study medications is ignored. [treatment policy strategy]
 - Non-optimal compliance is ignored. [treatment policy strategy]
 - Withdrawal due to lack of efficacy or adverse events. Baseline observation carried forward (BOCF) is used to impute missing data [hypothetical strategy].
 - Missing data without withdrawal or withdrawal due to reasons other than lack of efficacy or adverse events. Multiple imputations using randomized treatment-based Markov Chain Monte Carlo is used to impute missing data [hypothetical strategy].
- Population-level summary:
 - Difference in the mean CFB in tCFS in the study eye at Day 57 between NOV03 and saline.
 - Difference in the mean CFB in Dryness Score (VAS) at Day 57 between NOV03 and saline.

The primary comparison in this trial will be between NOV03 versus saline at Day 57. The primary efficacy endpoints (e.g. CFB in total corneal fluorescein staining [NEI scale] and Dryness Score) will be tested using hierarchical fixed sequence testing and summarized descriptively (n, mean, standard deviation, median, min, and max) and analyzed separately using an ANCOVA model with terms for baseline value, and treatment.

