6.5.7.3 Primary Efficacy Analyses

The primary comparisons in this trial will be between NOV03 versus saline at Day 57 in the FAS with available data per subject using the following estimands

- Endpoint:
 - CFB in tCFS in the study eye at Day 57
 - CFB of Dryness Score (VAS) at Day 57
- Intercurrent event:
 - Discontinuation of study medications is ignored. [treatment policy strategy]
 - Non-optimal compliance is ignored. [treatment policy strategy]
 - Withdrawal due to any reason. Missing data not imputed. [hypothetical strategy if overall study discontinuation rate is <5%]
- Population-level summary:
 - Difference in the mean CFB in tCFS in the study eye at Day 57 between NOV03 and saline
 - Difference in the mean CFB of Dryness Score (VAS) at Day 57 between NOV03 and saline

If the overall study discontinuation rate in the FAS is \geq 5% then the primary analysis will be based on imputation methodology using the following estimands:

• Endpoint:

Protocol Number: 904

- CFB in tCFS in the study eye at Day 57
- CFB of Dryness Score (VAS scale) at Day 57

• Intercurrent event:

- Discontinuation of study medications is ignored. [treatment policy strategy]
- Non-optimal compliance is ignored. [treatment policy strategy]
- Withdrawal due to lack of efficacy or adverse events: baseline observation carried forward (BOCF) is used to impute missing data [hypothetical strategy if overall study discontinuation rate ≥5%]
- Missing data without withdrawal or withdrawal due to reasons other than lack of efficacy or adverse events: multiple imputations using randomized treatment-based Markov Chain Monte Carlo (MCMC) is used to impute missing data [hypothetical strategy if overall study discontinuation rate ≥5%]
- Population-level summary:
 - Difference in the mean CFB in tCFS in the study eye at Day 57 between NOV03 and saline
 - Difference in the mean CFB of Dryness Score (VAS scale) at Day 57 between NOV03 and saline

The primary comparison in this trial will be between NOV03 versus saline at Day 57. The primary efficacy endpoints (e.g. CFB in total corneal fluorescein staining [NEI scale] and Dryness Score) will be tested using hierarchical fixed sequence testing and summarized descriptively (n, mean, standard deviation, median, min, and max) and analyzed separately using an ANCOVA model with terms for baseline value, and treatment.

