Least squares mean for each treatment group and for the difference between treatment groups will be presented from each model together with two-sided p-values (used for primary inference) and 95% confidence intervals.

Sample SAS ANCOVA code:

```
PROC GLM DATA=INDATA;
CLASS <TREATMENT>;
MODEL <ENDPOINT>=<TREATMENT> <BASELINE>;
LSMEANS <TREATMENT> / CL ALPHA=0.05;
LSMEANS <TREATMENT> / PDIFF CL ALPHA=0.05;
RUN;
```

Additional robustness analyses will include repeating the primary analysis on the PPS; the FAS imputing missing data using last observation carried forward (LOCF); the FAS imputing missing data using MCMC multiple imputation methodology under different assumptions of missingness (at random and not at random) each using 30 imputed values.

Sample SAS MCMC MI (missing at random):

```
PROC MI DATA=INDATA SEED=97656 OUT=OUTDATA MINIMUM=0 MAXIMUM=3 ROUND=1 NIMPUTE=30;
MCMC INITIAL=EM;
```

```
BY <TREATMENT>;
VAR <BASELINE> <PARAMETER>;
```

Where <PARAMETER> has 5 levels and refers to the CFS for each region (inferior, superior, central, temporal, and nasal).

Sample SAS MCMC MI (not missing at random):

```
PROC MI DATA=INDATA SEED=36797 OUT=MDATA MINIMUM=0 MAXIMUM=3 ROUND=1
NIMPUTE=30;
MCMC IMPUTE=MONOTONE;
VAR <BASELINE> <PARAMETER>;
RUN;

PROC MI DATA=MDATA SEED=38549 OUT=OUTDATA2 MINIMUM=. 0 0 MAXIMUM=. 3 3
ROUND=. 1 1;
CLASS <TREATMENT>;
MONOTONE REG(<PARAMETER>=<BASELINE> / DETAILS);
MNAR MODEL(<PARAMETER> / MODELOBS=(<TREATMENT>='Saline'));
VAR <TREATMENT> <BASELINE> <PARAMETER>;
RUN;
```

Where <PARAMETER> has 5 levels and refers to the CFS for each region (inferior, superior, central, temporal, and nasal).

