6.5.8.6.1 Imputation Method for Efficacy Endpoints

The primary analysis will be completed on the FAS with available data per subject, assuming the overall study discontinuation rate is \leq 5%. If the overall study discontinuation rate is \geq 5% then the primary analysis will be based on the primary imputation methodology as defined Section 6.5.7.3 and the available data analyses will become robustness analyses.

Additionally, robustness analyses will include repeating the primary analysis on the per protocol set (PPS); the FAS imputing missing data using last observation carried forward (LOCF); the FAS imputing missing data using Markov Chain Monte Carlo (MCMC) multiple imputation methodology under different assumptions of missingness (at random and not at random) each using 30 imputed values.

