7 INDEX OF PLANNED TABLES, FIGURES, AND LISTINGS

Title
Overall Disposition and Subject Accountability – FAS
Overall Disposition and Subject Accountability – PPS
Overall Disposition and Subject Accountability – SAF
Overview of Analysis Sets – Randomized Subjects
Reasons for Exclusion from Study Populations – Randomized Subjects
Major Protocol Deviations – FAS
Demographic and Baseline Characteristics – FAS
Demographic and Baseline Characteristics – PPS
Demographic and Baseline Characteristics – SAF
Baseline Ocular Characteristics – FAS
Baseline Ocular Characteristics – PPS
Baseline Ocular Characteristics – SAF
Study Eye Ocular Medical History – FAS
Fellow Eye Ocular Medical History – FAS
Subject Level Ocular Medical History – FAS
Non-ocular Medical History – FAS
Study Eye Ocular Concomitant Medications – FAS
Fellow Eye Ocular Concomitant Medications – FAS
Subject Level Ocular Concomitant Medications – FAS
Non-ocular Concomitant Medications – FAS
Study Medication Exposure and Compliance – SAF
Analyses of Change from Baseline tCFS and Dryness Score (VAS) at Day 57 – FAS
Analyses of Change from Baseline tCFS and Dryness Score (VAS) at Day 57 – PPS
Robustness Analyses of Change from Baseline tCFS and Dryness Score (VAS) at Day 57 (Discontinuation Rate ≥5%) – FAS
Sensitivity Analyses of Change from Baseline tCFS and Dryness Score (VAS) at Day 57 – FAS
Analyses of Secondary Efficacy Endpoints – FAS
Sensitivity Analyses of Secondary Efficacy Endpoints – FAS
Analysis of Dryness Score (VAS) – FAS
Sensitivity Analysis of Dryness Score (VAS) – FAS
Analysis of Study Eye tCFS – FAS

- 14.2.6.2 Analysis of Fellow Eye tCFS – FAS
- 14.2.6.3 Sensitivity Analysis of Study Eye tCFS – FAS
- Sensitivity Analysis of Fellow Eye tCFS FAS 14.2.6.4
- 14.2.7.1 Analysis of Study Eye Central Sub-region CFS (NEI scale) – FAS
- Analysis of Fellow Eye Central Sub-region CFS (NEI scale) FAS 14.2.7.2
- 14.2.7.3 Sensitivity Analysis of Study Eye Central Sub-region CFS (NEI scale) – FAS
- 14.2.7.4 Sensitivity Analysis of Fellow Eye Central Sub-region CFS (NEI scale) – FAS
- 14.2.7.5 Analysis of Study Eye Inferior Sub-region CFS (NEI scale) – FAS
- 14.2.7.6 Analysis of Fellow Eye Inferior Sub-region CFS (NEI scale) – FAS
- 14.2.7.7 Sensitivity Analysis of Study Eye Inferior Sub-region CFS (NEI scale) – FAS
- Sensitivity Analysis of Fellow Eye Inferior Sub-region CFS (NEI scale) FAS 14.2.7.8
- Summary of Study Eye CFS by Sub-region (NEI scale) FAS 14.2.8.1

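### The only printed multiple-imputation code predicts from baseline alone and fits staining scores only, and the ≥5% discontinuation branch names no imputation variables

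*Protocol*

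**What the plan says.** **Printed code.** Protocol 10.4.3 gives the missing-at-random (MAR) program after the words "The imputation model, for each visit, under the assumption of missing". It runs by treatment with bounds 0 and 3, rounding to 1 and 30 imputations. SAP 6.5.7.3 prints the same program as sample code with the variable list "VAR <BASELINE> <PARAMETER>" and the note "Where <PARAMETER> has 5 levels and refers to the CFS for each region (inferior, superior, central, temporal, and nasal". The saline-based not-at-random program has the same list; its second step sets bounds for treatment, baseline and one region, so it handles one region at a time.

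**Status of the code.** In the SAP it follows the sentence that begins "Additional robustness analyses will include repeating the primary analysis on the PPS", so it belongs to the robustness analyses. SAP 6.5.8.6.1 lists another of these, "the FAS imputing missing data using last observation carried forward (LOCF". The robustness analyses repeat the primary analysis, which has two endpoints. The SAP table index has an entry "Robustness Analyses of Change from Baseline tCFS and Dryness Score (VAS) at Day 57", marked there for the ≥5% case.

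**The ≥5% branch.** Withdrawals for lack of efficacy or adverse events get BOCF. For other missing data, Protocol 10.4.5 says "Multiple imputations using randomized treatment-based Markov Chain Monte Carlo is used to impute missing data" and SAP 6.5.7.3 says "multiple imputations using randomized treatment-based Markov Chain Monte Carlo (MCMC) is used to impute missing data". Neither gives variables, bounds, a seed or a number of imputations, and neither points to the printed code. The secondary endpoints inherit this branch (Protocol 10.4.6, SAP 6.5.7.4.1).

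**Data available.** Staining and all VAS items are collected at Days 15 and 29 (Protocol 8.4.1). Under SAP 6.5.8.2, an early-termination visit between scheduled visits counts as unscheduled, so for a dropout the interim visits are usually the only scheduled post-baseline scores.

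**The concern.** MI improves on an available-data analysis when the imputation model holds information that the analysis model lacks. Here the MAR program uses arm and baseline, and so does the ANCOVA. The interim scores, which best predict Day 57 and may explain why a subject left, are absent. The MAR run is therefore not an independent check on dropout related to interim response.

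The code also cannot be run sensibly for the Dryness Score (second primary) or VAS burning/stinging (third secondary). A 0-3 bound does not fit a scale on which randomization is stratified at 70.

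The stakes are highest in the ≥5% branch. The plan assumes 10% discontinuation, twice the switch, so on its own assumption the analysis with no stated MI variables is primary for both primary endpoints and all four secondaries. The variables should be fixed before unmasking.

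**Working it through.** **Inputs.** From Protocol 10.3: difference -1.0 and SD 2.8 for tCFS, -10 and 28 for Dryness, 250 evaluable and 280 randomized per arm, 10% discontinuation. The documents give no correlations between visits, dropout mechanism, dropout timing or BOCF share. These are my assumptions: residual correlations given baseline of 0.65 (Days 15-29), 0.6 (Days 29-57, varied 0.4-0.75) and 0.5 (Days 15-57), and logistic dropout with log-odds 0.5 / 1.0 / 1.5 per SD of the score. The total score is treated as continuous, without region-level bounds or rounding.

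**1. The plan's figures.** SE = 2.8 × √(2/250) = 0.250. Power = Φ(1.0/0.250 - 1.96) = Φ(2.03) = 97.9%, and 0.979² = 95.8%. Both are reproduced. 250/0.9 = 278 per arm, against 280 planned. Nothing below changes them. The switch is 0.05 × 560 = 28 subjects; the assumed rate gives 0.10 × 560 = 56.

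**2. Baseline-only MI against available-data ANCOVA.** In 2000 simulated trials the two tCFS estimates correlated 0.998, and their difference had SD 0.015. A separate simulation on the Dryness scale gave estimates within about 0.02 points and SEs within about 0.01.

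**3. Bias formula.** Baseline-only MI places an arm's missing residuals at its observed mean. With missing fraction p, correlation ρ between the Day 29 and Day 57 residuals, SD σ and mean standardized Day 29 score δ among dropouts, the arm mean shifts by

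p/(1-p) × ρ × σ × δ.

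At p = 0.10 the logistic model gives δ = 0.44 / 0.817 / 1.095. Then 0.111 × 0.6 × 2.8 × δ = 0.08 / 0.15 / 0.20.

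**4. Bias in the tCFS difference** (10% missing per arm unless stated; log-odds 0.5 / 1.0 / 1.5)

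| Dropout assumption | Baseline-only MI | MI with Days 15 and 29 |
|---|---|---|
| Random, or equal dependence at equal rates | 0.00 | 0.00 |
| One common rule on raw Day 29 change, 10% overall | 0.01 / 0.04 / 0.07, toward zero | about 0 |
| Log-odds 1.0 in NOV03, 0.5 in saline | 0.07 | about 0 |
| One arm only, no BOCF | 0.08 / 0.15 / 0.20 | about 0 |
| Same, correlation 0.4 | 0.05 / 0.10 / 0.14 | about 0 |
| Same, correlation 0.75 | 0.10 / 0.19 / 0.26 | about 0 |
| Same, 5% missing | 0.04 / 0.08 / 0.11 | about 0 |
| One arm only, one third leaving before Day 15, one third after Day 15, one third after Day 29 | about 0.08 / 0.15 / 0.20 | 0.02 / 0.05 / 0.06 |
| One arm only, random half to BOCF, true difference 0, mean change -2 | 0.08 / 0.15 / 0.20 | 0.04 / 0.07 / 0.09 |

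The one-arm bias is away from zero if the arm is NOV03. In the staggered row, the interim visits remove about two thirds. In the BOCF row they remove about half; the rest comes from BOCF and lies outside this point. LOCF in the one-arm, no-BOCF case is off by 0.05 / 0.09 / 0.12 in the opposite direction.

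**5. Cost of leaving the variables open.** With random 10% dropout, 280 per arm and 1500 trials per setting, baseline-only and interim-visit MI estimates in the same trial differ with SD 0.052 (0.017 from imputation noise alone). Significance differs in 1.2% of trials at a true -1.0 and 6.7% at -0.5 (noise alone 0.3% and 2.1%; with half BOCF 0.7% and 5.1%).

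**6. Dryness.** 28/2.8 = 10, so each bias is ten times larger on the VAS, against an SE of 2.5. In the separate simulation, with 15% dropout in saline, 5% in NOV03 and log-odds 1.0, baseline-only MI shifted the difference toward zero by 0.65 / 1.07 / 1.57 points at between-visit correlations 0.4 / 0.6 / 0.8. With interim visits the shift was at most 0.06. With 10% in both arms, every method was within 0.1 point.

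**The case against.** **An all-visit MAR analysis is already planned.** The repeated-measures model (Protocol 10.4.5, SAP 6.5.7.6.1 and 6.5.7.6.2) includes treatment by visit and an unstructured covariance, and it covers both primaries and the quantitative secondaries. This stands, and it rules out the reading that no planned analysis uses the interim data. But that model is a sensitivity analysis and does not fill the ≥5% branch. Its sample ESTIMATE statement has no Day 57 term, though the model text allows one.

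**BOCF removes the response-related dropouts from MI.** This stands in part. If 5% response-related dropouts in NOV03 go to BOCF and 5% unrelated ones go to MI, the two MI models differ by at most 0.001. That split is the favourable extreme, as the no-BOCF case is the unfavourable one; the documents support neither.

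**For tCFS the model can be inferred.** SAP 6.5.8.6.1 refers to 6.5.7.3 for the primary imputation, and that section prints by-treatment MCMC code. The inference is reasonable, but the code is labelled robustness and the branch does not cite it. A reader might conclude that the ≥5% primary analysis will use baseline-only MI and is biased; the documents do not say so.

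**The table index alone does not prove that a VAS imputation is planned.** Correct. Its title is limited to the ≥5% case, where the available-data analyses themselves become robustness analyses. The firmer support is the text that repeats the primary analysis under MI. Missing VAS code and a missing cross-reference would by themselves be only missing detail.

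**Conclusion.** The point holds in a limited form. The printed MAR imputation uses baseline alone within arm and nearly repeats the available-data ANCOVA. The code cannot serve the VAS endpoints. The branch that becomes primary at 5% discontinuation states no imputation variables; below 5%, available data are primary and that branch is not used.

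Bias is not established. It is about zero under random dropout or equal dependence at equal rates, and 0.01-0.07 tCFS points, toward zero, under a common rule. It is 0.08-0.20 at correlation 0.6 only if dropout depends on response in one arm and BOCF takes none of it. Against the planning SE of 0.25, the last range is material and the others are small. A reader might infer that the trial's result would be shifted toward NOV03 by up to 0.20; that rests wholly on assumed dropout that differs between arms. Sample size and power are unaffected. The change is worth making because it is cheap and gives a better method, not because a bias has been shown.

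**What to change.** In Protocol 10.4.3 and 10.4.5 and SAP 6.5.7.3, specify one MI approach for both the MAR robustness analysis and the MI part of the ≥5% branch:

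- MCMC by treatment with baseline, Day 15, Day 29 and Day 57 in the variable list, 30 imputations, a stated seed and Rubin's rules.
- Staining: impute so that total and central scores stay consistent, for example by imputing the regions with their interim visits and then summing. Separate models for total and central scores could give imputed values that conflict.
- Dryness and VAS burning/stinging: impute on the VAS scale, without the 0-3 bounds or ROUND=1.
- Subjects withdrawn for lack of efficacy or adverse events: apply the plan's existing BOCF rule after MI to every missing post-withdrawal visit that is analysed, including Day 15, since the Day 15 secondaries inherit the rule.
- An explicit reference from the ≥5% branch in both documents to this model.
- A VAS version of the saline-based not-at-random model with the same visits.

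The cost is wording and more programming, with no new data. The change does not help subjects who leave before Day 15 and does not alter the effect of BOCF.

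### Read literally, the printed MI code imputes each corneal region on its own, bounded to 0–3 and rounded, so imputed tCFS totals vary too little, sit too high, and give a modestly understated MI standard error

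*Protocol*

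**What the plan says.** tCFS is the sum of five regional scores of 0–3 in the study eye, maximum 15 (SAP 6.5.4.1.7).

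Protocol 10.4.3 gives PROC MI code for two robustness analyses, missing at random (MAR) and missing not at random (MNAR), each with 30 imputations. The variable list in the MAR step is "VAR <BASELINE> <PARAMETER>", "where PARAMETER has 5 levels and refers to the corneal fluorescein staining score for each region (inferior, superior, central, temporal, and nasal"). SAP 6.5.7.3 prints the same code, with the options "MINIMUM=0 MAXIMUM=3 ROUND=1 NIMPUTE=30" in the MAR step. In the second MNAR step the limits become three-entry lists, "OUT=OUTDATA2 MINIMUM=. 0 0 MAXIMUM=. 3 3", and the regression is "MONOTONE REG(<PARAMETER> = <BASELINE> / DETAILS").

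If overall discontinuation is 5% or more, Protocol 10.4.5 and SAP 6.5.7.3 make imputation part of the primary analysis. Withdrawals for lack of efficacy or adverse events get BOCF. For the other missing values, "Multiple imputations using randomized treatment-based Markov Chain Monte Carlo is used to impute missing data [hypothetical strategy"]. No code is attached to that sentence. Neither document says how an imputed total is formed from imputed regions.

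**The concern.** Regions of one cornea would be expected to vary together. If each is imputed from its own baseline with no reference to the other four, the residuals are drawn independently and the covariance terms are missing from the variance of their sum. Imputed totals are then less variable than real ones. Both components of the MI variance shrink, and the confidence interval charges too little for the missing data.

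The bounds and rounding are a separate fault. More of the normal draws fall below 0 than above 3 when scores are low. Redrawing them lifts the imputed mean, and lifts it more in the arm with the lower scores, which pulls the treatment difference toward zero.

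The accuracy of the MAR and MNAR robustness analyses of the first primary endpoint is at stake. So is that of the primary analysis itself if this code is used once discontinuation reaches 5%. The plan assumes 10% (Protocol 10.3).

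**Working it through.** **1. The plan's own figure.** Inputs from Protocol 10.3: 250 per arm, difference −1.0, SD 2.8, two-sided 0.05. SE = 2.8 × √(2/250) = 0.2504. Power = Φ(1.0/0.2504 − 1.960) = Φ(2.03) = 97.9%, as stated. 0.979² = 95.8% and 250/0.90 = 278, given as about 280. The sample size is not in question.

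**2. How many variables the code imputes per run.** The lists "MAXIMUM = . 3 3 ROUND = . 1 1" have three entries and match treatment, baseline and parameter one for one. The 0–3 limit on the baseline entry shows that it is a regional score, because eligible totals are 4–11 (Protocol 5.3). The MNAR regression has the region's baseline as its only predictor. The literal model is therefore one region per run.

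**3. Why the spread falls.** For five regions with residual SD s and common residual correlation r, Var(sum) = 5s²(1 + 4r). Independent draws give 5s². The SD ratio is 1/√(1 + 4r): 1.00 at r = 0, 0.75 at r = 0.2 and 0.62 at r = 0.4.

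**4. Effect on the standard error.** Simulation, 250–400 trials per scenario, 280 per arm, 30 imputations, ANCOVA on baseline and treatment, pooling by Rubin's rules. Assumed, not in the documents: five 0–3 regions with latent between-region correlation 0.2, 0.4 or 0.6, regional means giving a true difference of about −1.0, data missing completely at random, and all missing values sent to MI. Correlation 0.4 gives a change-from-baseline SD of about 2.8, the plan's value. In this table, values are rounded before the bounds check.

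| Latent correlation | Missing | SE, region by region | SE, total imputed directly | Shortfall |
|---|---|---|---|---|
| 0.2 | 10% | 0.2021 | 0.2109 | 4.2% |
| 0.4 | 10% | 0.2206 | 0.2336 | 5.6% |
| 0.6 | 10% | 0.2369 | 0.2536 | 6.6% |
| 0.4 | 5% | 0.2209 | 0.2274 | 2.9% |
| 0.4 | 20% | 0.2217 | 0.2501 | 11.4% |

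Bounding the raw values before rounding gives an SE of 0.2203 in the last row, 11.9% short.

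Rubin's formula, T = W + (1 + 1/30)B, shows the source in the second row. Region by region: 0.04629 + 1.0333 × 0.00234 = 0.0487, square root 0.221. Total directly: 0.04892 + 1.0333 × 0.00554 = 0.0546, square root 0.234. Both W and B are too small. The SE of 0.221 equals the full-data SE (0.221), although the available-data SE is 0.233. The 95% half-width is 1.96 × 0.2206 = 0.432 instead of 1.96 × 0.2336 = 0.458.

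Against the estimator's own empirical SD in that run (0.2290) the shortfall is 3.7%. With 400 trials that SD carries Monte Carlo error of about 1/√800 = 3.5%.

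**5. Effect on the imputed values and the contrast (correlation 0.4).** At 10% missing, the SD of imputed totals is about 1.9 in saline and 1.8 in NOV03, against true values of 2.9 and 2.7. Imputed means are too high by about 0.2 (saline) and 0.4 (NOV03) if values are rounded before the bounds check, or 0.4 and 0.7 if raw values are bounded. The difference moves from −0.99 to −0.98 or −0.97. At 20% missing it moves from −0.996 to −0.968 or −0.941.

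**6. The most generous reading.** With all five regions in one list but bounds and rounding kept, 10% missing and correlation 0.4, the imputed SD in saline is 2.45 against 2.83 for the total imputed directly. The SE is 0.2282 against 0.2336, 2.3% short.

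**The case against.** **It is only sample code, and one region at a time is an inference.** The SAP does label the code as a sample, and the MAR step uses single limits that would also suit a list of all five regions. But Protocol 10.4.3 introduces it as the imputation model itself, and SAP 6.6 records no change. The MNAR step fits only one region per run. Even the generous reading leaves the bounds and rounding error.

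**The size rests on an assumed correlation, and not all missing data go to MI.** This stands. With no residual correlation only the small bounds and rounding error remains. Some withdrawals get BOCF, and Protocol 8.4.2 encourages subjects who stop treatment to keep attending. If half of a 10% loss went to MI, the SE error would be about 3%.

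**Nothing changes at the planned effect.** This also stands. At 10% missing and correlation 0.4, z is 0.98/0.221 = 4.4 with the literal code and 0.99/0.234 = 4.2 with the total imputed directly. The shift in the contrast is against NOV03.

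**Two stronger readings that a reader might infer.** First, that the primary analysis is known to use this code. The documents print it for the robustness analyses and do not link it to the 5% branch. Second, that the SE would be too large because the printed seed ("PROC MI DATA=INDATA SEED=97656 OUT=OUTDATA MINIMUM=0 MAXIMUM=3 ROUND=1 NIMPUTE=30") locks the five draws together. Neither document says that five runs share one seed. The bounds also force redraws, which use different numbers of random draws in each region and separate the streams. In a small check (assumed regional means 0.7–1.4, residual SD 0.78, one shared seed), the correlation between regional draws fell from 1.00 without bounds to near zero with them.

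**Conclusion.** The point holds for the code as printed. Imputed tCFS totals vary too little and are biased upward, more so in the lower-scoring arm. Under assumed latent correlations of 0.2–0.6, with all missing data imputed by MI, the SE is about 4–7% too small at 10% missing. At correlation 0.4 it is about 3% too small at 5% missing and 11–12% at 20%. The contrast moves about 0.01–0.03 toward zero at 10% and up to about 0.06 at 20%. These are upper-side figures, because BOCF takes part of the missing data.

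This is a modest error in the reported precision, and the documents do not support reading it as a threat to the trial's conclusion. It certainly affects the MAR and MNAR robustness analyses. Whether it affects the primary analysis at 5% or more discontinuation is unstated, but no other treatment-based MCMC specification is available for that branch.

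**What to change.** In Protocol 10.4.3 and SAP 6.5.7.3:

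- Put all five regional baselines and all five regional post-baseline scores in one joint variable list, by randomized treatment for MAR, with matching joint code for MNAR.
- Delete MINIMUM, MAXIMUM and ROUND.
- Sum the regions to tCFS after imputation.
- Use the same imputed central score for cCFS at Day 57. That secondary endpoint follows the primary imputation method when discontinuation is 5% or more (Protocol 10.4.6, SAP 6.5.7.4.1), so imputing only the total would leave it without imputed values.
- State that this model is the MI used for tCFS in the 5%-or-more primary analysis.

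At 10% missing and correlation 0.4, imputing the regions jointly or the total directly, without bounds or rounding, gave a NOV03 imputed-total SD of 2.8 (true 2.7), a difference of −0.99 and an SE of 0.234.

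The cost is a few lines of code and matching text in both documents before unmasking. Imputed scores may be non-integer or slightly out of range, which is harmless in the ANCOVA.

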10.4.2 Unit of Analysis

For efficacy endpoints, the unit of analysis will be the study eye as defined by the following:
Study Eye: Eyes are eligible for analysis if they meet all of the inclusion criteria. In the case that both eyes are eligible for analysis, the worst eye shall be chosen, and this will be defined as the eye with worse (higher) total corneal staining at Visit 1. If the total corneal staining is the same in both eyes then the right eye will be selected as the study eye.

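### Step 2 of the printed not-at-random tCFS imputation lacks `BY _Imputation_` and `NIMPUTE`, so as printed it does not give the stated 30 completed datasets

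*Protocol*

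**What the plan says.** Both documents plan multiple imputation of missing tCFS under two missingness assumptions. SAP 6.5.8.6.1 gives the number: "at random and not at random) each using 30 imputed values". Protocol 10.4.3 and SAP 6.5.7.3 say the same.

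The at-random program is one call, and it prints the number in the step that writes its output: "PROC MI DATA=INDATA SEED=97656 OUT=OUTDATA MINIMUM=0 MAXIMUM=3 ROUND=1 NIMPUTE=30" (SAP 6.5.7.3).

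The not-at-random program has two steps, printed alike in both documents:

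- Step 1, "PROC MI DATA=INDATA SEED=36797 OUT=MDATA", carries `NIMPUTE=30` and fills values only as far as a monotone pattern.
- Step 2, "PROC MI DATA=MDATA SEED=38549 OUT=OUTDATA2", imputes what is still missing from a regression fitted to saline observations. Its PROC statement has bounds and rounding but no `NIMPUTE`. It is followed only by CLASS, MONOTONE REG, MNAR and VAR statements, so there is no BY.

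The two documents give the code a different status. Protocol 10.4.3 introduces it with "The imputation model, for each visit, under the assumption of missing not at" (random) and equates the model with the code. The SAP heads its copy "Sample SAS MCMC MI (not missing at random".

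The SAP index of tables (section 7) lists the output under a title with a condition, cut here before the percent sign: "Robustness Analyses of Change from Baseline tCFS and Dryness Score (VAS) at Day 57 (Discontinuation Rate ≥5".

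**The concern.** After step 1, MDATA holds 30 copies of the trial. Step 2 has to complete each copy once, and nothing in the printed step tells it to. Without a BY statement it treats the 30 copies as one large trial. Without `NIMPUTE` the number of completed versions is a software default that the documents do not give.

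The risk lies in what happens to OUTDATA2 afterwards. Neither document prints a by-imputation analysis or a pooling step. If OUTDATA2 is analysed by the index that step 2 writes, each analysis dataset contains every subject 30 times. The standard error then shrinks with no added information, and the not-at-random check looks far more convincing than the data allow. This is the printed check that fills missing values from the saline arm, so a falsely narrow interval would undermine its purpose.

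The table is likely to be produced. It is tied to discontinuation of 5% or more, and the sample size section assumes 10%.

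**Working it through.** **Inputs.** From protocol 10.3: 560 randomised subjects (280 per arm), tCFS standard deviation 2.8, two-sided alpha 0.05 and 10% discontinuation. From protocol 10.4.3 and SAP 6.5.7.3: 30 imputations. The step 2 default, m, is not in the documents and is varied as an assumption. A second assumption is that a step without BY treats its input as one dataset.

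**Row count.** Step 1 gives 30 × 560 = 16,800 rows. The intended result after step 2 is 30 datasets of 560, again 16,800 rows. As printed, step 2 gives m datasets of 16,800 rows:

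| m (assumed) | Datasets indexed by step 2 | Rows in each | Total rows |
|---|---|---|---|
| 1 | 1 | 16,800 | 16,800 |
| 5 | 5 | 16,800 | 84,000 |
| 25 | 25 | 16,800 | 420,000 |
| 30 | 30 | 16,800 | 504,000 |

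The stated structure is not reproduced for any m. Even m = 30 gives 30 datasets in which each subject appears 30 times.

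**Analytic size if analysed by the step 2 index.**

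- Standard error with one row per subject: 2.8 × √(2/280) = 0.237.
- With 30 rows per subject: 0.237 / √30 = 0.043. The ratio is √30 = 5.48.
- Null rejection of a nominal 5% test: 2 × (1 − Φ(1.96/√30)) = 0.72.

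**Simulation.** The set-up was 280 per arm, five regional scores rounded to 0–3, baseline total 4–11, and ANCOVA residual SD 2.9. Baseline was complete and 10% of Day 57 values were missing at random. Each region was imputed by a saline-based regression on its own baseline. The change in tCFS was analysed by ANCOVA and pooled by Rubin's rules. Results for 2,000 null trials with m = 5:

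| How OUTDATA2 is used | Standard error | Null rejection |
|---|---|---|
| Corrected: each copy completed once, 30 datasets pooled | 0.2437 | 4.6% |
| As printed, every copy analysed separately and pooled | 0.2434 | 4.5% |
| As printed, only one of the 30 copies kept | 0.2445 | 4.3% |
| As printed, analysed by step 2 index | 0.0445 | 70.7% |

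The ratio of the corrected standard error to that of the last row is 0.2437 / 0.0445 = 5.48. It is 5.49 with m = 25 (500 trials), 5.48 with 5% missing and 5.46 with 15% missing (1,000 trials each). With a true effect of about −1.0, the mean estimate is −0.932 under all four uses.

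A separately coded, simpler simulation with a continuous score and no bounds gave null rejection of 5.3% with the correction (400 runs). By the step 2 index it gave 67.5% (m = 5, 400 runs) and 66% (m = 25, 200 runs).

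**The case against.** The case against has four parts.

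- **The code is a template.** The SAP labels it a sample, and both copies contain placeholders, so neither can literally be run. No by-imputation or pooling code is printed for any multiple-imputation analysis, the at-random one included. The stated 30 is clear, and a competent programmer would probably add the missing lines.
- **The 5.48-fold error needs a second mistake.** Someone would have to analyse 30 rows per subject, against the plan's own rule: "For efficacy endpoints, the unit of analysis will be the study eye as defined by the following". Under the other two uses of the printed output, the standard error is within 0.3% of the corrected one.
- **The mistake would be hard to miss.** The three-entry bounds suggest one call per corneal region, with five outputs to be merged into a total. Subject and step 2 index would not be a unique key in that merge. A descriptive n near 16,800 in place of 560 would also stand out.
- **Part of the argument rests on software behaviour.** The documents give neither the default m nor the treatment of an imputation index already present in the input.

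Most of this stands, and it limits the weight of the point. It does not remove it. The protocol presents the code as the model, not as a sample. The unit-of-analysis rule shows that the printed step is inconsistent with the plan, but it does not correct the step. The at-random program prints both its BY statement (by treatment) and `NIMPUTE=30`, so the step 2 omissions are not just the general level of detail. The mismatch with 30 datasets of 560 holds for any default.

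**Conclusion.** The concern holds and is minor. As printed in both documents, step 2 cannot deliver the stated 30 separately completed datasets of 560 subjects.

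The size depends on an unprinted analysis step. The standard error ranges from essentially correct (copies analysed separately and pooled) to 5.48 times too small (analysed by the step 2 index). The upper figure is what happens if the structure written by step 2 is followed, and it departs from the study-eye unit of analysis. The simulated figures also rest on complete baselines and missingness at random.

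The reach is the confidence interval and p-value of one robustness analysis of tCFS, in a table tied to discontinuation of 5% or more. The 0–3 bounds and the five corneal regions confine the printed program to tCFS, so nothing follows for the Dryness Score. The primary ANCOVA, the separate imputation rule for the primary analysis at 5% or more discontinuation, the testing hierarchy, the power and the point estimate are unaffected.

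**What to change.** In protocol 10.4.3 and SAP 6.5.7.3, add `NIMPUTE=1` to the second PROC MI statement and a `BY _Imputation_` statement to that step. Each of the 30 step 1 datasets is then completed once. State that the primary ANCOVA is run on each completed dataset, with one record per subject, and that the 30 results are pooled.

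The cost is one option and one BY line in each document, plus a sentence on analysis and pooling. Data collection, sample size, the imputation model and the primary test do not change.
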